### 7.3.1. Subgroup Analyses for Primary Endpoint

Subgroups will be formed based on the following participant characteristics and baseline variables for those participants whose data are available:

- Sex (male, female)
- Geographic region
- Baseline anti-IgE biologic use

The primary efficacy endpoint will be summarized using descriptive statistics based on the FAS Population for the above subgroups.

## 7.4. Analysis of the Secondary Efficacy Parameters

The secondary efficacy analysis will be based on the FAS.

### 7.4.1. Categorical Secondary Efficacy Endpoints

The odds ratios for the proportion of participants with  $UAS7 \leq 6$  at Week 12 in each of the povorcitinib groups and the placebo group and the corresponding 95% CIs will be assessed using logistic regression with treatment and stratification factor (previous use of an anti-IgE biologic [yes or no]). All participants who have not achieved  $UAS7 \leq 6$  at Week 12, as well as all participants who are missing postbaseline values, will be defined as nonresponders for the nonresponder imputation analysis.

[figure not shown]
The odds ratios for the proportion of participants with  $UAS7 = 0$  at Week 12 in each of the povorcitinib groups and the placebo group and the corresponding 95% CIs will be assessed using logistic regression with treatment and stratification factor (previous use of an anti-IgE biologic [yes or no]). All participants who have not achieved  $UAS7 = 0$  at Week 12, as well as all participants who are missing postbaseline values, will be defined as nonresponders for the nonresponder imputation analysis.

[figure not shown]
[figure not shown]
#### **7.4.2. Time-to-Event Secondary Efficacy Endpoints**

Time to first achievement of  $UAS7 \leq 6$  during the PC period is defined as the time from the date of randomization until the earliest date of achieving  $UAS7 \leq 6$  during the PC period. Participants who have not achieved  $UAS7 \leq 6$  during the PC period will be censored at the last available  $UAS7$  measurement time. Summaries of time to first achievement of  $UAS7 \leq 6$  during the PC period will be assessed using the Kaplan-Meier method, and the estimated Kaplan-Meier curve will be displayed graphically.

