### 3.1. Randomization

The study will enroll approximately 136 participants in a 1:1:1:1 randomization ratio, stratified at baseline by previous anti-IgE biologic use (yes or no), into 1 of 4 treatment groups during the PC period.

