### 7.1. General Considerations

[figure not shown]
[figure not shown]
All by-visit analyses for the EXT-Evaluable Population will include the follow-up period if the data are available or unless otherwise specified. Likewise, unless otherwise stated, the strata identified in the randomization process will be used in all efficacy analyses.

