### Tables

Table No.	Title	Population	Standard
1.1.1	Analysis Populations	All Screened	X
1.1.1.1	Screening Disposition	All Screened	X
1.1.2.x	Summary of Participant Disposition During the PC Period	FAS/EXT-Evaluable	X
1.1.3	Summary of Number of Participants Enrolled by Country and Site	FAS	X
1.1.4.x	Summary of Protocol Deviations During the PC Period	FAS/EXT-Evaluable	X
1.2.x	Summary of Demographics and Baseline Characteristics During the PC Period	FAS/EXT-Evaluable	X
1.3.1	Summary of Baseline Disease Characteristics	FAS	X
1.4.1	Summary of Prior Medications	FAS	X
1.4.2	Summary of Concomitant Medications During the PC Period	FAS/EXT-Evaluable	X
1.5.1	Summary of General Medical History	FAS	X
1.5.2	Summary of Chronic Spontaneous Urticaria Disease History	FAS	X
Efficacy			
2.1.1.x	Summary and Analysis of UAS7 by Visit	FAS/EXT-Evaluable	
2.1.2	Summary of UAS7 by Visit and Sex	FAS	
2.1.3	Summary of UAS7 by Visit and Geographic Region	FAS	
2.1.4	Summary of UAS7 by Visit and Baseline Anti-IgE Biologic Use	FAS	
2.2.1.1.x	Summary and Analysis of Proportion of Participants Who Achieved UAS7 $\leq$ 6 (Controlled Disease) by Visit	FAS/EXT-Evaluable	
2.2.1.2	Summary of Time to First Achievement of UAS7 $\leq$ 6 (Controlled Disease) During the PC Period	FAS	
2.2.1.3.x	Summary and Analysis of Proportion of Participants With UAS7 = 0 by Visit	FAS/EXT-Evaluable	
2.3.1.1.x	Summary of Change From Baseline in HSS7 by Visit	FAS/EXT-Evaluable	
2.3.1.2.x	Summary of Proportion of Participants With HSS7 = 0 by Visit	FAS/EXT-Evaluable	
2.3.1.3	Summary of Time to First Achievement of HSS7 MID ( $\geq$ 5-Point) Improvement From Baseline Up to Week 36	FAS	

Table No.	Title	Population	Standard
2.3.1.4	Summary of Change From Baseline in Weekly HSS7 During the Post-Treatment Follow-Up Period (EOT2 to EOS)	Post-Treatment-Evaluable	
2.3.2.1.x	Summary of Change from Baseline in ISS7 by Visit	FAS/EXT-Evaluable	
2.3.2.2.x	Summary of Proportion of Participants with ISS7 = 0 by Visit	FAS/EXT-Evaluable	
2.3.2.3	Summary of Time to First Achievement of ISS7 MID ( $\geq$ 5-Point) Improvement From Baseline Up to Week 36	FAS	
2.3.2.4	Summary of Change From Baseline in Weekly ISS7 During the Post-Treatment Follow-Up Period (EOT2 to EOS)	Post-Treatment-Evaluable	
2.3.4.1	Summary of Time to First Achievement of UAS7 $\geq$ 9.5-Point Improvement From Baseline Up to Week 36	FAS	

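### Time to first UAS7 ≤ 6 is a secondary endpoint, but the plan specifies no dose-versus-placebo effect estimate or between-group confidence interval for it

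*SAP*

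**What the plan says.** Protocol Table 5 and SAP Table 1 list three secondary endpoints: UAS7 ≤ 6 at Week 12, UAS7 = 0 at Week 12, and time to first UAS7 ≤ 6 during the placebo-controlled period.

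- **Time-to-event endpoint.** SAP 7.4.2 defines the event and the censoring, then says that summaries "will be assessed using the Kaplan-Meier method, and the estimated Kaplan-Meier curve will be displayed graphically". Protocol 10.4.2 plans the same. Neither mentions a hazard ratio, a log-rank test, a difference in medians or the stratum.
- **Two binary endpoints.** In SAP 7.4.1, the odds ratios against placebo and their 95% CIs are "assessed using logistic regression with treatment and stratification factor".
- **Table list (SAP Appendix A).** Table 2.2.1.2 is titled "Summary of Time to First Achievement of UAS7" ≤ 6. Its binary counterpart, Table 2.2.1.3.x, is titled "Summary and Analysis of Proportion of Participants With UAS7 = 0 by Visit", and Table 2.2.1.1.x is also a summary and analysis. Figure 4.1.4 is a single Kaplan-Meier figure with no stratum in its title.
- **Strata.** SAP 3.1 describes randomization as "stratified at baseline by previous anti-IgE biologic use (yes or no), into 1 of 4 treatment groups during the PC period". SAP 7.1 sets the default: "unless otherwise stated, the strata identified in the randomization process will be used in all efficacy analyses".
- **Intervals and multiplicity.** SAP 3.2 applies no multiplicity adjustment and reports two-sided 95% CIs where appropriate.

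**The concern.** A secondary endpoint on speed of disease control is there to show whether any dose gets participants to control sooner than placebo, by how much, and with what uncertainty. Kaplan-Meier estimates describe each arm separately. Without a named effect measure there is nothing to which a between-group interval could attach, so the comparison is left to the reader's inspection of four curves of about 34 participants each. A hazard ratio added after the sponsor is unblinded at the primary analysis would be post hoc.

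The plan treats its other two secondary endpoints differently and gives no reason. Protocol 10.4 describes the final analysis as being without statistical comparison to placebo, which suggests that such comparisons belong in the Week 12 analysis, where this endpoint sits.

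The stratum raises a second question. Protocol 2.2.1 justifies it on the ground that participants with earlier biologic exposure may have more severe disease and may respond differently. An analyst following 7.4.2 does not know whether the 7.1 default calls for separate curves by stratum, a stratified comparison or nothing.

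**Working it through.** **1. The plan's own figure.** The documents give no power, event count or rate for this endpoint. The only power stated in the design is for the primary test: at least 0.85 with 34 per group, SD 13, means of -8 and -17, one-sided 2.5% (protocol 10.1). Simulating MCP-Mod with the six candidate models at doses 0, 15, 45 and 75 mg (1,000,000 draws, critical value 2.191, df 132) gives a minimum of 0.847, under the linear model. The stated figure reproduces, and nothing below bears on it.

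**2. What is specified for each secondary endpoint.**

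| Endpoint | Effect measure v placebo | 95% CI for it | Stratum in the text |
|---|---|---|---|
| UAS7 ≤ 6 at Week 12 | Odds ratio | Yes | Yes |
| UAS7 = 0 at Week 12 | Odds ratio | Yes | Yes |
| Time to first UAS7 ≤ 6 | None | None | Not mentioned |

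Three doses against placebo make three possible contrasts for the third row; none is specified.

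**3. What a hazard ratio would deliver.** The rates here are assumptions: a proportion p0 on placebo and p1 on active treatment reach UAS7 ≤ 6 by Week 12, with proportional hazards, no dropout and 34 per arm.

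- HR = ln(1 − p1) / ln(1 − p0)
- Events E = 34 × (p0 + p1)
- SE of ln HR = √(4/E)
- Two-sided 5% log-rank power = Φ(|ln HR| × √E / 2 − 1.96)

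Example, 20% v 50%: HR = ln 0.5 / ln 0.8 = 3.11; E = 34 × 0.70 = 23.8; SE = √(4/23.8) = 0.41; 95% CI = exp(1.13 ± 1.96 × 0.41), about 1.4 to 6.9; power 0.79.

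| p0 v p1 | HR | Events | 95% CI | Log-rank power | Power, Week 12 proportions |
|---|---|---|---|---|---|
| 15% v 35% | 2.65 | 17.0 | 1.02-6.86 | 0.52 | 0.48 |
| 15% v 45% | 3.68 | 20.4 | 1.54-8.76 | 0.84 | 0.78 |
| 20% v 40% | 2.29 | 20.4 | 0.96-5.45 | 0.46 | 0.44 |
| 20% v 50% | 3.11 | 23.8 | 1.39-6.94 | 0.79 | 0.75 |
| 25% v 50% | 2.41 | 25.5 | 1.11-5.24 | 0.60 | 0.57 |
| 30% v 55% | 2.24 | 28.9 | 1.08-4.64 | 0.58 | 0.55 |

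For 80% power, E = 4 × (1.96 + 0.84)² / (ln HR)², which is 66, 38 and 27 events for HR 2, 2.5 and 3. The contrast is therefore imprecise, but on the same assumed rates it is about as informative as a comparison of Week 12 proportions, which the plan does make.

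**4. How much the stratum matters.** Log-rank tests were simulated at 34 v 34 with a placebo rate of about 20% and HR 2.5, 4,000 runs per setting. The prior-biologic share was 20% or 40%, and the hazard ratio between strata 1.0, 0.5 or 0.3 (all assumed). Power was 0.48-0.54 unstratified and 0.52-0.54 stratified. The largest gain was from 0.48 to 0.52, with a 40% share and a stratum hazard ratio of 0.3.

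**The case against.** The best defence is that the descriptive choice is deliberate. Protocol and SAP agree, and the table titles separate summary from analysis. The study is a proof of concept whose formal inference rests on the dose-response test. That is a legitimate phase 2 position, and it stands: the plan is consistent between its two documents. But 7.4.2 does not state it, and the plan does give comparative estimates for the other two secondary endpoints.

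Three stronger readings are tempting, and the documents do not support them.

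- **A reader might infer that 7.4.2 breaks SAP 7.1.** The 7.1 rule holds only unless otherwise stated, and other efficacy displays, such as the primary-endpoint subgroups in 7.3.1, are purely descriptive. The stratum is unaddressed in 7.4.2, not excluded in breach of a rule.
- **A reader might infer that the comparison is missing because the stratum is.** Randomized arms can be compared validly without it. The comparison is missing because no effect measure is named.
- **A reader might infer that the trial will say nothing about timing or uncertainty.** Kaplan-Meier summaries are planned as well as the curve. Table 2.2.1.1.x and Figure 4.1.2.1 give the UAS7 ≤ 6 proportion by visit. The general CI rule in SAP 3.2 may put intervals on the per-arm estimates, and the table shells are in a separate document. These give partial information on speed, but none is a specified between-group estimate for this endpoint.

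The remedy also has limits. Intervals will be wide. The event comes from a rolling 7-day score that is available only after Day 7 (SAP 7.2.1.1), so proportional hazards has to be checked.

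**Conclusion.** The gap is real and minor. For one of three secondary endpoints, none of the three dose-versus-placebo contrasts has a specified effect estimate or between-group CI. This follows from the text alone and needs no assumption. How the 7.1 default on strata applies to this endpoint is a second, smaller omission, worth at most about 0.04 in power in the settings simulated.

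The value of filling the gap rests on assumed rates. At 15-30% on placebo and 35-55% on active treatment, each contrast would have about 17-29 events and power of 0.46-0.84, with upper confidence limits roughly 4 to 7 times the lower ones (4.64/1.08 = 4.3; 6.86/1.02 = 6.7). Such estimates would support description with stated uncertainty, not a firm claim for any one dose. The primary analysis, its power and the two binary secondary endpoints are unaffected.

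**What to change.** Add to SAP 7.4.2, in substance: a Cox proportional-hazards model with treatment as the factor, stratified by previous anti-IgE biologic use (yes or no), will give the hazard ratio and 95% CI for each povorcitinib dose against placebo. Stratified log-rank p-values will be reported as nominal, and the proportional-hazards assumption will be checked. Keep the Kaplan-Meier summaries and curve, and retitle Table 2.2.1.2 as a summary and analysis. This also settles how 7.1 applies.

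The cost is one sentence or two and one table. No new data are needed, because SAP 7.2.1.1 already derives UAS7 day by day for time-to-event endpoints. The downsides are three more comparisons without multiplicity control (in line with SAP 3.2), a modelling assumption to defend, and wide intervals.

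If the sponsor prefers to keep the endpoint descriptive, the minimum is a sentence in 7.4.2 saying so and stating that the 7.1 default on strata does not apply to it. That removes the ambiguity but leaves the endpoint without a comparison.

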#### **7.5. Analysis of Exploratory Efficacy Variables**

All exploratory efficacy variables will be summarized using descriptive statistics (see [Table 1](#)).

## 9. SAFETY AND TOLERABILITY

[Appendix A](#) provides a list of data displays. Sample data displays are included in a separate document.

### 9.1. General Considerations

The analyses in this section will be provided for the Safety Population during the PC period, the EXT-Evaluable Population during the EXT period, and for participants who received only povorcitinib 15, 45, or 75 mg during the overall period unless otherwise specified. Summary tables may be replaced with listings when appropriate; for instance, an AE frequency table may be replaced with a listing if it only contains a few unique PTs reported on relatively few participants.

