The time interval of 12 weeks for the PC period and the primary endpoint is sufficient to allow for assessment of both itch and angioedema resolution and is aligned with several other clinical trials in CSU, thereby imposing no increased time burden for participants entering this study versus others. Data of povorcitinib in HS demonstrate a treatment effect on itch at 2 weeks, with continued reduction of itch symptoms over 12 weeks (Kirby et al 2022c). Clinical studies of other JAK inhibitors for the treatment of AD reported reduction of itch early in treatment and continued improvements in disease severity at 16 weeks (Erikson et al 2021).

Findings from case studies reported on the use of tofacitinib in CSU (Mansouri et al 2022) suggest patients with the most severe symptoms may require a longer period of treatment and justifies a 24-week EXT period in the present study, which will include participants with CSU that is inadequately controlled on H1 antihistamines, who may have experienced treatment failure on or after monoclonal antibody therapy, or with CSU that is more difficult to treat.

After completion of the PC period, participants will continue the study in the 24-week EXT period, which allows participants initially randomized to placebo to receive active drug and further evaluation of the efficacy and safety of povorcitinib. The 60-day, post-treatment, follow-up period allows for assessment of persistence of the effect of povorcitinib in CSU without compromising participants who wish to enroll in other ongoing studies or need to receive alternative treatment for their CSU.

Details of the objectives and endpoints are included in Section 3. The primary efficacy endpoint of change from baseline in the UAS7 at Week 12 has been chosen because it is a validated

questionnaire and has been used in pivotal trials in CSU to measure reduction in CSU disease severity.

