10. STATISTICS

10.1. Sample Size Determination

Approximately 136 participants will be randomly assigned to 4 treatment groups (placebo or povorcitinib 15, 45, or 75 mg) in a 1:1:1:1 ratio.

The sample size is based on the primary efficacy endpoint, the change in weekly UAS7 score from baseline at Week 12. Based on a Phase 2b study (Maurer et al 2022), the mean change in UAS7 score at Week 12 is assumed to be -8 in the placebo group and -17 in the povorcitinib 75-mg group, with a common STD of 13. A sample size of 34 participants per group is sufficient to test for the presence of a dose-response relationship, based on the MCP-mod approach (Bretz et al 2005, Pinheiro et al 2013).

This sample size provides a minimum power of 0.85 to detect a dose effect at a 1-sided 2.5% significance level with the linear, log-linear, E_{max} , and quadratic models prespecified as candidates to characterize the underlying dose-response curve for povorcitinib on the mean change in weekly UAS7 score at Week 12. The set of candidate dose-response models and their corresponding dose-response curves are shown in Table 12 and Figure 2, respectively.

[figure not shown]
Table 12: Prespecified Candidate Models

Model	$f(d, \theta)^a$	$f^0(d, \theta)^b$	Initial Value(s) for Parameter(s)
Linear	$E_0 + \delta d$	d	Not applicable
Linear log-dose	$E_0 + \delta \log(d + 1)$	$\log(d + 1)$	Not applicable
E_{max1}	$E_0 + \frac{E_{max}d}{ED_{50} + d}$	$\frac{d}{ED_{50} + d}$	$ED_{50} = 20$
E_{max2}			$ED_{50} = 30$
Sigmoid- E_{max}	$E_0 + \frac{E_{max}d^h}{ED_{50}^h + d^h}$	$\frac{d^h}{ED_{50}^h + d^h}$	$ED_{50} = 30, h = 2$
Quadratic	$E_0 + \beta_1 d + \beta_2 d^2$	$d + \frac{\beta_2}{ \beta_1 } d^2$	$\delta = \frac{\beta_2}{ \beta_1 } = -0.0083$

^a d is dose ($d = 0$ for placebo group), θ refers to the vector of model parameters, E_0 is the placebo effect for all candidate models (0.1), E_{max} is the maximum treatment effect over placebo, ED_{50} is the dose that gives 50% of the maximum effect for E_{max} model.

^b Standardized model.

Figure 2: Prespecified Dose-Response Curves

For a reference of different assumptions of STD of the change in UAS7 score from baseline at Week 12, the sample sizes and the corresponding minimum power to detect a significant dose-response signal at a 1-sided 2.5% significance level are provided in [Table 13](#).

Table 13: Samples Sizes and Minimum Power Across the 6 Prespecified Candidate Models Under Different Assumptions of Standard Deviation

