#### **5.3.2. Safety Population**

The Safety Population includes all participants who received at least 1 dose of study drug. Treatment groups for this population will be determined according to the actual treatment the participant received regardless of assigned study drug treatment.

All safety analyses for the PC and overall period will be conducted using the Safety Population.

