2.3.4.2	Summary of Proportion of Participants Who Achieved UAS7 $\leq$ 6 at Week 12 and Maintained or Improved Their Response at Every Visit Through to Week 36 or EOT2	FAS	
2.3.4.3	Summary of Proportion of Participants Who Achieved UAS7 = 0 at Week 12 and Maintained Their Response at Every Visit Through to Week 36 or EOT2	FAS	

Table No.	Title	Population	Standard
2.3.13.1	Summary of Proportion of Participants Requiring Treatment of Chronic Spontaneous Urticaria With Corticosteroids From Baseline Up to Week 36	FAS	
2.3.13.2	Summary of Proportion of Participants Requiring Rescue Treatment of Chronic Spontaneous Urticaria With Additional Second-Generation H1 Antihistamines From Baseline Up to Week 36	FAS	
2.3.13.3	Summary of Time to First Use of Rescue Medication From Baseline Up to Week 36	FAS	
2.3.13.4	Summary of Proportion of Participants Using Rescue Medication During the Post-Treatment Follow-Up Period (EOT2 to EOS)	Post-Treatment-Evaluable	
2.3.13.5	Summary of Time to Use of Rescue Medication During the Post-Treatment Follow-Up Period (EOT2 to EOS)	Post-Treatment-Evaluable	
Safety			
3.1.1.x	Summary of Exposure During the PC Period	Safety/EXT-Evaluable	X
3.1.1.3	Summary of Exposure for Participants Who Received Only Povorcitinib Throughout Study Participation (Overall Period)	Safety	X
3.1.2.x	Summary of Study Drug Compliance During the PC Period	Safety/EXT-Evaluable	X
3.2.1.x	Overall Summary of Treatment-Emergent Adverse Events During the PC Period	Safety/EXT-Evaluable	X
3.2.1.3	Overall Summary of Treatment-Emergent Adverse Events for Participants Who Received Only Povorcitinib During Study Participation	Safety	X
3.2.2.x	Summary of Treatment-Emergent Adverse Events by MedDRA System Organ Class and Preferred Term During the PC Period	Safety/EXT-Evaluable	X
3.2.2.3	Summary of Treatment-Emergent Adverse Events by MedDRA System Organ Class and Preferred Term for Participants Who Received Only Povorcitinib During Study Participation	Safety	X
3.2.3.x	Summary of Treatment-Emergent Adverse Events by MedDRA Preferred Term in Decreasing Order of Frequency During the PC Period	Safety/EXT-Evaluable	X

Table No.	Title	Population	Standard
3.2.3.3	Summary of Treatment-Emergent Adverse Events by MedDRA Preferred Term in Decreasing Order of Frequency for Participants Who Received Only Povorcitinib During Study Participation	Safety	X

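### The only by-dose safety tables that span both treatment periods leave out placebo participants who cross to povorcitinib; an all-exposure set by dose should be added

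*SAP*

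**What the plan says.** After the 12-week placebo-controlled (PC) period, continuing placebo participants are assigned 1:1:1 to 15, 45 or 75 mg for the 24-week extension (Protocol 2.2.1 and 2.2.2). Protocol 2.2.1 says that the extension "allows participants initially randomized to placebo to receive active drug and further evaluation of the efficacy and safety of povorcitinib".

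SAP 5.2 sets three presentations by treatment group:

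- PC period: placebo, 15, 45 and 75 mg.
- Extension and post-treatment periods: six groups, with the three placebo-to-povorcitinib groups kept apart from the three continuing groups.
- Overall period (safety only): 15, 45 and 75 mg.

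SAP 5.3.2 states the population for the overall period without a restriction: "All safety analyses for the PC and overall period will be conducted using the Safety Population". SAP 9.1 then gives the overall-period analyses "for participants who received only povorcitinib 15, 45, or 75 mg during the overall period unless otherwise specified". SAP 6.4 (exposure), 9.2.1 (TEAE definition) and 9.2.2 (AE summaries) do the same. Appendix A follows suit: Table 3.1.1.3 for exposure and Tables 3.2.1.3 to 3.2.20.3 for adverse events are titled for the povorcitinib-only group, for example "Overall Summary of Treatment-Emergent Adverse Events for Participants Who Received Only Povorcitinib During Study Participation". Their listed population is Safety.

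The TEAE windows in SAP 9.2.1 also differ. The extension window closes at EOT2. The overall-period window for povorcitinib-only participants runs to EOS.

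**The concern.** The safety objective is the safety and tolerability of povorcitinib, and a crossover participant's 24 weeks on the drug bear on it. In the PC tables that person counts as placebo. In the extension tables the person sits in a column of about 11. The overall-period tables omit the person. Appendix A lists no table that puts all exposed participants under the dose they received, and no exposure-adjusted rate is planned.

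What is at stake is precision for uncommon events. Protocol 9.6.1 names serious infection, zoster, malignancy, MACE and thromboembolism as events of special interest. In a trial of this size, what can be said about them by dose depends mainly on how many people were exposed and for how long.

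The windows add a gap. A crossover participant's event in the roughly 60-day follow-up falls after the extension window closes, and the overall window does not apply to that participant. SAP 5.2 announces post-treatment summaries and SAP 5.3.4 defines a population for them, but the Appendix A tables assigned to that population are efficacy and rescue-medication tables. The event would reach the listings, and no listed TEAE table.

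**Working it through.** **Inputs**

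- Sample size and allocation, Protocol 10.1: "Approximately 136 participants will be randomly assigned to 4 treatment groups (placebo or povorcitinib 15, 45, or 75 mg) in a 1:1:1:1 ratio".
- Group size, Protocol 10.1: "A sample size of 34 participants per group is sufficient to test for the presence of a dose-response relationship".
- Crossover allocation 1:1:1, Protocol 2.2.1 and 2.2.2.
- Periods of 12 and 24 weeks, Protocol Table 2.
- Dropout before Week 12: not given in the documents, so it is an assumption, shown from 0% to 30%.

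**The plan's own figure.** 136 / 4 = 34 per group. Simulating the MCP-Mod test with the six candidate models, maximum effect 9, SD 13 and 34 per group gives a critical value of about 2.19 and a minimum power of 0.846 to 0.848, against the stated 0.85. This confirms the group size used below and has no other bearing on the point.

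**Headcount excluded.** With 3 x 34 = 102 randomized to povorcitinib and placebo dropout p before Week 12, the excluded share is 34(1 - p) / [102 + 34(1 - p)].

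| p | Crossovers | Per dose | Share of exposed |
|---|---|---|---|
| 0% | 34 | 11.3 | 25.0% |
| 5% | 32.3 | 10.8 | 24.1% |
| 10% | 30.6 | 10.2 | 23.1% |
| 20% | 27.2 | 9.1 | 21.1% |
| 30% | 23.8 | 7.9 | 18.9% |

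**Treatment time excluded.** Povorcitinib throughout: 102 x 36 = 3672 person-weeks. Crossovers: 34 x 24 = 816. Share: 816 / (3672 + 816) = 816 / 4488 = 18.2%. With 20% dropout in the placebo group only: 27.2 x 24 = 652.8, and 652.8 / 4324.8 = 15.1%. With the same 20% dropout in every arm midway through the PC period the share is 17.6%.

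**Precision, weighting crossovers by exposure.** If risk scales with time on drug, a 24-week crossover counts as 24/36 of a 36-week participant. With no dropout:

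- Per dose: 34 + 11.33 x 24/36 = 41.6, against 34.
- All doses: 102 + 34 x 24/36 = 124.7, against 102. SAP 5.2 lists no total column, so this is a sum over the dose columns.

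The zero-event one-sided 95% upper bound is 1 - 0.05^(1/n):

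- Per dose: 8.4% at n = 34, about 7.0% at 41.6.
- All doses: 2.9% at n = 102, about 2.4% at 124.7.

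The chance of at least one case of an event with 1% risk is 1 - 0.99^n: 64% at n = 102, about 71% at 124.7. With 20% placebo dropout the effective n is 102 + 27.2 x 24/36 = 120.1, and the 71% becomes about 70%.

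**The case against.** **No data are lost.** A reader might infer that crossover safety data are discarded. They are not. Crossovers belong to the EXT-Evaluable Population, have their own dose columns, and are covered by the extension AE and AESI tables. The AE listings include every event whatever its timing. This stands in full.

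**The counts can be added by hand.** The povorcitinib-only and crossover groups do not overlap, so a reader can sum the two numerators and denominators for a dose. That works for on-treatment events. It fails after EOT2, where one window has closed and the other runs to EOS.

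**Separation is defensible.** Crossovers have completed 12 weeks on placebo, start povorcitinib later and have 24 rather than 36 planned weeks on it. Keeping the originally randomized cohorts intact is sound. Person-year rates do not fully repair the difference either, because they assume a roughly constant hazard and can mislead for early-onset events. This justifies keeping the povorcitinib-only tables, but not the absence of an all-exposed set beside them.

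**No commitment is broken.** Protocol 10.4.3 promises descriptive tables, without pooling or exposure-adjusted rates. A reader might infer from Protocol 2.2.1 that the crossover was built to enlarge the by-dose safety sample. The text says only that it gives placebo participants active drug and allows further evaluation. Nor does the SAP rank the overall-period tables above the others.

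**SAP 5.3.2 against 9.1.** This can look like a contradiction, but Appendix A labels the povorcitinib-only tables as Safety, so they read naturally as a subset. The wording needs a clarifying sentence, no more.

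**Conclusion.** The point holds as a gap in presentation and precision. The cross-period by-dose exposure and AE tables omit up to 34 of 136 povorcitinib-exposed participants. The 25% is a ceiling that needs every placebo participant to cross over; assumed placebo dropout of 5% to 30% gives about 24% down to 19%. By treatment time the share is at most about 18%, provided the povorcitinib arms do not lose more follow-up than the placebo arm.

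Including crossovers would bring a modest gain: upper bounds of about 7.0% instead of 8.4% per dose and about 2.4% instead of 2.9% across doses, and about a 71% instead of a 64% chance of seeing a 1% event. These figures assume no dropout and risk proportional to time on drug. Counting crossovers as full participants (n = 136) would give 75%, but that ignores their shorter exposure. Neither sample size would settle by-dose risk for events as rare as MACE or malignancy.

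The restriction covers Table 3.1.1.3 and the AE tables 3.2.1.3 to 3.2.20.3. It does not cover every Appendix A table whose number ends in .3. The primary efficacy conclusion is unaffected.

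**What to change.** - In SAP 5.2, 9.1, 9.2.1 and 9.2.2, add a supplementary all-povorcitinib-exposure set with columns by dose received: 15 mg plus placebo-to-15 mg, and likewise for 45 and 75 mg.
- Start the count at the first povorcitinib dose (Day 1, or the first extension dose for crossovers) and run it to EOS. For crossovers use the extension safety baseline already defined in SAP 4.1.3.
- Report TEAEs, SAEs, AESIs and ECIs as n (%) and per 100 person-years. Extend the exposure summary in SAP 6.4 to supply the denominators, and list the tables in Appendix A.
- Keep the povorcitinib-only tables, and state in SAP 5.3.2 that they describe a subset of the Safety Population.

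The cost is SAP wording and some extra programming on data already collected. No visits or participants are added. Because the rates assume a roughly constant hazard, they should be read beside the period-specific tables.
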